### ***Recruitment***

Participants will be identified through routine NHS orthopaedic outpatient clinics at the participating centres, in accordance with the eligibility criteria by the clinical team. Potentially eligible patients will be highlighted by the research team who will provide patient information relating to the study, with adequate time for consideration of the relevant materials and discussion with the clinical team before consent is sought. Participants will be randomised on a 1:1 basis to receive either: mTKA or raTKA. A separate consent form will be provided for the MAL sub-study.

Recruitment is planned to take place over 36 months, with each participant followed for 12 months post-operatively. Due to the use of the Attune Medial Stabilized (MS) polyethylene insert, long-term observation will be conducted for a minimum of 10 years to evaluate survivorship and cross-validated with national registry data. The final phase of data analysis and dissemination will be conducted in year 5 of the study. The trial protocol is aligned with SPIRIT 2025 guidelines. The study conduct will be reported according to CONSORT 2025 guidelines.

### ***Eligibility***

Eligible participants will be aged 18 years or older, with a diagnosis of primary knee osteoarthritis requiring primary TKA. Participants must be suitable for either raTKA or mTKA, capable of providing written informed consent, and capable and willing to complete clinical and patient-reported outcome measures throughout the study period. (Figure 1)

Eligibility	
Inclusion Criteria	
	Aged >18 years
	Primary knee OA
	Requiring TKA
	Suitable for either raTKA or mTKA
	Capable to provide written informed consent
	Capable and willing to complete outcome measures throughout study period
Exclusion Criteria	
	Inflammatory arthritis
	Significant symptomatic hip, ankle, or contralateral knee OA
	Prior TKA or major injury or major surgery on the index knee
	Neuromuscular gait disorders
	BMI >45 kg/m 
	Coronal plane deformity >15° varus/valgus on pre-op HKA radiograph
	Fixed flexion deformity greater than 15°
	Bone loss likely to require non-standard implants (e.g. stems, augments)
	Severe deformity or ligament insufficiency likely to require constraint
	Inability to comply with the required follow-up assessments or complete PROMs
	Contraindications to any aspect of the surgical technique

**Fig 1.** *Eligibility criteria.*

OA: osteoarthritis, TKA: total knee arthroplasty, raTKA: robot-assisted TKA, mTKA: manual TKA, BMI: body mass index, PROMs: patient-reported outcome measures.

### ***Randomisation***

Participants will be randomised in a 1:1 ratio to receive either manual TKA or VELYS robot-assisted functional alignment TKA. Randomisation will be performed using a secure web-based system (Research Electronic Data Capture [REDCap], Vanderbilt University, USA) incorporating computer-generated permuted block randomisation, stratified by recruitment centre. Block sizes will be randomly varied and concealed to ensure allocation concealment. Following written informed consent and collection of baseline data, site research staff will enrol and randomise participants.

### ***Blinding***

The study is a randomised controlled trial with patient and outcome assessor blinding for the duration of trial conduct and follow-up period. It is not possible to blind surgeons given the nature of the interventions. Non-surgical clinical staff (e.g. ward nurses and allied health professionals) will be

blinded. Femoral and tibial tracker pins will be placed within the surgical incision, avoiding the need for accessory incisions in raTKA cases or sham incisions to aid blinding in mTKA cases. Documentation will be redacted appropriately to prevent inadvertent unblinding of clinicians. PROMs will be completed independently by participants. Radiographic assessments and biomechanical analyses will be performed by assessors who are blinded to treatment allocation. All study data will be anonymised and the study arm concealed before the conduct of data analysis.

Routine unblinding is not planned. Unblinding will be permitted only where knowledge of treatment allocation is considered necessary for urgent clinical management or participant safety. Any request for unblinding should be made by the treating clinician to the Chief Investigator or delegated medically qualified investigator. The reason for unblinding, the date, the person authorising it, and the person informed will be documented in the trial records. The Sponsor will be informed, and the event will be reviewed by the Trial Steering Committee. Wherever possible, unblinding of one participant will not result in unblinding of outcome assessors or the wider trial team.

### ***Retention and withdrawal of participants***

Participants have the right to withdraw from the trial at any point and for any reason, without providing an explanation. Withdrawal from the study will not affect their routine clinical care. The Principal Investigators (or delegate) may also withdraw participants from the study intervention if it is deemed in their best interest, including but not limited to:

- Development of a medical condition making continuation inappropriate;
- Adverse Events (AEs) or Serious Adverse Events (SAEs) that necessitate discontinuation;
- Significant protocol violations that compromise study integrity or participant safety;
- Participant request or non-compliance with study procedures.

Data collected up to the point of withdrawal will be retained and included in analyses, unless the participant specifically requests data removal in line with GDPR provisions. Participants who withdraw before randomisation or before any study procedures will be replaced to ensure an adequate sample size. Participants who withdraw after randomisation will not be routinely replaced, unless withdrawal rates threaten study power, in which case replacement will be considered. If

withdrawal occurs due to an AE or SAE, appropriate medical care will be provided and relevant safety follow-up conducted until the event has resolved or stabilised. All such cases will be reported in accordance with regulatory requirements. Participants will be informed of these arrangements during the consent process, and all efforts will be made to minimise the burden of continued safety follow-up for those who withdraw from the intervention arm of the study.

Follow-up will be promoted through alignment of study assessments with routine clinical care wherever possible, use of electronic, postal, telephone, or in-person data collection methods, and reminder contact from the research team for outstanding questionnaires or visits. Participants who discontinue the allocated intervention or deviate from the protocol will be invited to remain in follow-up unless they withdraw consent for further data collection. Where full follow-up is not possible, the study team will seek to collect a minimum dataset comprising the primary outcome where feasible, key safety outcomes including adverse events and reoperations, and relevant routine clinical data available from the medical record.

### ***Surgical technique***

A thigh tourniquet will be used for the full case until closure of the arthrotomy, and a medial parapatellar approach to the knee will be used in all cases. A cemented Attune prosthesis with medial stabilised (MS) polyethylene insert will be implanted in all patients. Perioperative care will be delivered in a standardised fashion in accordance with safe established practice and will not vary according to treatment arm.

### ***Manual TKA***

Participants randomised to this group will undergo manual TKA performed with conventional jig-based instrumentation using cemented Attune Knee System components (Johnson & Johnson MedTech) and a medial stabilised (MS) polyethylene insert. The aim will be to correct deformity towards a neutral limb alignment and achieve a TKA that is stable throughout the flexion-extension arc.

Extramedullary referencing will be used to align the proximal tibial resection perpendicular to the axis of the tibia. Intramedullary referencing will be used to align the distal femoral resection based on pre-operative planning and intra-operative assessment. Femoral axial alignment will be set initially at 3 degrees of external rotation relative to the posterior condylar axis, typically perpendicular to

Whiteside's line, and adjusted based on the flexion gap and patellar tracking. Measured bone resections will be made using the standard cutting guides for the Attune TKA system.

#### *VELYS robot-assisted functional alignment TKA*

Participants allocated to the raTKA group will undergo TKA using the VELYS system following a functional alignment (FA) strategy that uses technology-assisted intraoperative evaluation to restore ligament balance and stability throughout the flexion-extension arc while reconstructing the native kinematic axes of the pre-arthritis knee. This is achieved by precise assessment of the soft tissue envelope using the VELYS system with subsequent adjustments to the planned bone resections to achieve an optimally sized, aligned, and balanced TKA using minimal bone resections to accommodate the thinnest necessary polyethylene insert and minimising the need for soft tissue releases. Bone resections and implant positioning will be guided by the VELYS Robot-assisted Solution within safe target ranges: tibial resection 0° to 7° varus; overall limb alignment (HKA) 173°–183° (i.e. HKA between 7° varus and 3° valgus). The femoral and tibial robotic arrays will be placed intra-incisional according to the standard VELYS technique to avoid the need for additional incisions.

It is possible to achieve FA either from a mechanically-aligned pre-operative plan, where bone resections are planned to produce neutral alignment in the coronal plane, or a kinematically-aligned pre-operative plan, where anatomical bone resections are planned to resurface the native anatomy. The latter accounts for bone loss, and thus restores the constitutional [pre-arthritis] limb alignment and joint line obliquity. FA is then achieved by technology-assisted intraoperative assessment of the soft tissues and subsequent adjustments made to the planned resections to achieve a balanced knee. Soft tissue release is only utilised as a last resort if satisfactory alignment or balance is not achieved by modifying the bone resections alone. For consistency in this study, all raTKA patients will be treated according to a KA-based FA philosophy. VELYS-acquired intra-operative data will be captured for correlation with post-operative outcomes.

#### *Technical consistency*

The Surgical Lead will chair a surgeon's group to review the surgical and perioperative techniques to ensure consistency of practice across all participating sites. Any deviations from the defined surgical protocol will be documented and will require prior approval by the CI and site PIs, Trial Steering Committee (TSC) and Research Ethics Committee (REC). Adherence to the intervention protocol will be monitored via surgical records and VELYS system logs.

### ***Outcomes***

The primary outcome will be the change in Forgotten Joint Score (FJS) at two timepoints, preoperatively versus 6 months post-surgery. Secondary outcome measures will include PROMs; clinical outcomes; functional, physiological, and technology-enabled activity measures; health service and economic outcomes; technical surgical/radiographic measures, and biomechanical outcomes using motion analysis laboratory assessment. A dedicated motion analysis laboratory (MAL) study will be conducted as a nested sub-study. (Figure 2)

Outcomes	
Primary measure	Change in FJS [pre-surgery, 6 months] 
Secondary Measures	Change in FJS [pre-surgery, 6 weeks, 12 months] Absolute FJS [6 weeks, 6 months, 12 months] OKS [pre-operative, 6 weeks, 6 months, 12 months]  EQ-5D-5L [pre-operative, 6 weeks, 6 months, and 12 months]  Satisfaction Score (NRS, Likert scale) [6 weeks, 6 months, 12 months]  Pain score (VAS) [6 weeks, 6 months, 12 months]  PROM anchor questions  Functional, physiological and technology-enabled activity measures Change in radiographic parameters Alignment measures (HKA, JLO, CPAK, component size and position)  Surgical time (preparation, case, tourniquet & turnaround) NASA TLX & clinician experience (after 1st and every 5th case)  Health service resource utilisation (clinical contacts, analgesic use)

**Fig 2.** Primary and secondary outcome measures. Time points are relative to date of surgery.

FJS: Forgotten Joint Score, OKS: Oxford Knee Score, EQ-5D-5L; EuroQol EQ-5D 5-Level, NRS: numeric rating scale, VAS: visual analogue scale, HKA: hip-knee-ankle axis, JLO: joint line obliquity, CPAK: coronal plane alignment of the knee, NASA TLX: NASA Task Load Index.

### **Subgroup analyses**

Predefined subgroup analyses will explore potential differences in outcomes according to: age; sex; BMI; socioeconomic deprivation level; primary compartment involved (medial, lateral, or patellofemoral); CPAK group and restoration; VELYS-acquired intra-operative data (for raTKA group).

These subgroup analyses will extend the primary models by including interaction terms and will be considered exploratory. A generalised linear model will be applied, incorporating allocation group, age, site, surgeon, gender, BMI ( $\geq 35$  kg/m^2), and the primary compartment affected (medial, lateral, or patellofemoral) as covariates. Both fixed- and random-effects modelling will be employed to assess robustness. Sensitivity analyses will explore model assumptions and include both modelling approaches. Other subgroup analyses may be pre-specified as appropriate.

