### ***Data collection***

Study data will be collected using a bespoke portal on REDCap (Research Electronic Data Capture, Vanderbilt University, USA) at predefined time points, aligned with the clinical care pathway. An option for in-person, postal, and telephone collection will also be available to participants at each time point. (Table 1)

At the pre-operative baseline visit, participants will complete the PROMs questionnaires (FJS, OKS, EQ-5D-5L, satisfaction scores, and pain score). Pre-operative bilateral hip-knee-ankle (HKA) radiographs will be obtained to assess coronal alignment, joint line obliquity, and enable CPAK classification. For participants enrolled in the motion analysis laboratory (MAL) sub-study, a baseline assessment will be conducted during the same hospital visit.

During surgery, data will be collected relating to surgical workflow and efficiency (including case time, tourniquet time, operating room preparation and turnaround times). For the raTKA group, VELYS-acquired intra-operative data will be collected. Data from inpatient medical records will be collected. Routine postoperative radiographs will be taken in line with standard clinical practice.

At six weeks post-operatively, participants will complete the PROMs questionnaires. In addition, participants will complete a health service resource use questionnaire, which will capture clinical service contacts (including frequency and reason) and analgesic use during the follow-up period.

At six months post-operatively, participants will complete the FJS (primary outcome), and secondary PROMs questionnaires, and post-operative bilateral HKA radiographs will be obtained to assess implant positioning and limb alignment. A further health service resource use questionnaire will also be completed. MAL sub-study participants will undergo a repeat assessment.

At 12 months post-operatively, participants will complete the full set of PROMs, along with a final health service resource use questionnaire.

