### ***Statistical analysis***

All analyses will adhere to CONSORT reporting standards. A detailed statistical analysis plan will be finalised with the Trial Steering Committee before any formal analyses are undertaken. Baseline characteristics will be summarised to assess comparability between treatment groups. Simple descriptive statistics will follow standard conventions, including means and standard deviations or medians and interquartile ranges as appropriate for continuous variables, and counts and percentages for categorical data.

The primary analysis will examine differences between the two intervention groups (using an intention-to-treat approach) with regard to their change in FJS (preoperatively versus 6 months post-surgery). A Student's independent t-test will be used to compare mean scores between groups. Assumptions of normality and equality of variances will be assessed using diagnostic plots and Levene's test. If variances are unequal, the Welch's t-test will be applied. The results will be reported as mean differences with 95% confidence intervals and p-values.

Secondary outcomes will be analysed similarly, appropriate to the type and distribution of the data. Categorical outcomes, such as patient satisfaction and complication rates, will be compared between groups using the chi-square test. If any expected cell count is less than five, Fisher's exact test will be applied. Effect sizes will be reported alongside these comparisons using risk ratios or odds ratios with 95% confidence intervals to provide a measure of the magnitude and precision of differences between groups.

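### CPAK restoration is a result of the allocated surgery, so it cannot serve as a treatment-effect subgroup; VELYS data, present in one arm only, can support only a within-arm association

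*Protocol*

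**What the plan says.** The Subgroup analyses section of the protocol gives one list of predefined factors: age, sex, BMI, deprivation, primary compartment, and then "CPAK group and restoration; VELYS-acquired intra-operative data (for raTKA group"). The next sentence covers the list without exception: "These subgroup analyses will extend the primary models by including interaction terms and will be considered exploratory". The model follows: "A generalised linear model will be applied, incorporating allocation group, age, site, surgeon, gender, BMI" and compartment.

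On timing, Randomisation states: "Following written informed consent and collection of baseline data, site research staff will enrol and randomise participants". Under Data collection, "Pre-operative bilateral hip-knee-ankle (HKA) radiographs will be obtained to assess coronal alignment, joint line obliquity, and enable CPAK classification". The post-operative HKA radiographs come at six months, and VELYS data are recorded during surgery in the robot arm only.

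On alignment, the Manual TKA section says "The aim will be to correct deformity towards a neutral limb alignment". The VELYS section says "For consistency in this study, all raTKA patients will be treated according to a KA-based FA philosophy", and explains that a kinematic plan restores the constitutional alignment and joint line obliquity. Outcomes (Fig 2) also lists post-operative alignment and CPAK as secondary outcomes.

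**The concern.** A treatment-by-subgroup interaction has a randomised interpretation only when the subgroup is fixed before allocation. Pre-operative CPAK group meets that condition. CPAK restoration does not: it compares the post-operative knee with the pre-operative one, and one arm aims to restore constitutional alignment while the other aims towards neutral. A restored manual knee and a restored robotic knee reach that state by different routes, so the patients behind them need not be alike. The VELYS item has a different problem, because there is no manual-arm counterpart with which to form an interaction.

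The abstract names subgroup effectiveness among the NICE evidence domains that the trial addresses. A finding that the robot works better when CPAK is restored could be read as a randomised subgroup effect when it is an observational contrast.

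**Working it through.** **1. Reference figures.** The protocol states no figure for the subgroup analyses. The yardstick is its sample size: 2 × (1.645 + 0.842)² × 24² / 7² = 145.4, so 146 per group (147 stated, power 80.4%). Then 147 / 0.85 = 173, as stated. The 7-point MCID and 147 evaluable per arm are used below.

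**2. When each factor is fixed.**

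| Factor | Known | Arms | Fixed before randomisation? |
|---|---|---|---|
| Age, sex, BMI, deprivation, compartment | Baseline | Both | Yes |
| CPAK group | Pre-operative radiograph | Both | Yes |
| CPAK restoration | Post-operative radiograph | Both, with different targets | No |
| VELYS data | During surgery | Robot only | No |

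**3. VELYS data.** Let A = 1 for robot and V be a VELYS measure, with model b0 + b1·A + b2·V + b3·A·V. If V is coded 0 in the manual arm, A·V equals V in every row and the design matrix has rank 3 for 4 coefficients (confirmed numerically). If V is left missing in the manual arm, only robot rows remain, A is constant and the arm effect is lost. Either way b3 cannot be estimated. This needs no assumption.

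**4. Restoration, equal selection in both arms.** Assume a latent prognostic factor U ~ N(0,1), logit P(restored) = a(arm) + g·U, outcome β·U plus noise, and no effect of treatment or of restoration. The bias in the arm difference (robot minus manual) within stratum r is

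β × { E[U | r, robot] − E[U | r, manual] }.

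Restoration rates, odds ratios per SD (exp g) and β are all assumed; none is in the protocol. Example with 15% restored in the manual arm, 80% in the robot arm, odds ratio 3 and β = 7.2: the mean of U among the restored is 0.806 (manual) and 0.186 (robot), giving 7.2 × (0.186 − 0.806) ≈ −4.5. Among the not restored it is −0.142 and −0.742, giving 7.2 × (−0.600) = −4.3.

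| Restored, manual / robot | OR per SD, β | Bias, restored | Bias, not restored | Interaction |
|---|---|---|---|---|
| 15% / 80% | 1.5, 4.8 | −1.24 | −1.23 | −0.01 |
| 15% / 80% | 2, 7.2 | −3.06 | −3.01 | −0.06 |
| 15% / 80% | 3, 7.2 | −4.47 | −4.32 | −0.15 |
| 30% / 60% | 1.5, 4.8 | −0.57 | −0.56 | −0.01 |
| 30% / 60% | 3, 7.2 | −1.99 | −1.88 | −0.10 |
| 40% / 60% | 1.5, 4.8 | −0.37 | −0.37 | 0.00 |
| 40% / 60% | 3, 7.2 | −1.28 | −1.28 | 0.00 |

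The within-stratum bias runs from about 0.4 to 4.5 points. The interaction is the difference between the two bias columns and is nearly nil; at 15% / 50% with odds ratio 3 and β = 7.2 it reaches −0.49. At 15% / 80% the cells would hold about 22 and 125 manual patients (147 × 0.15 and the rest) and 118 and 29 robot patients.

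**5. Restoration, selection differing by arm** (15% / 80% restored).

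| OR manual / robot, β | Bias, restored | Bias, not restored | Interaction |
|---|---|---|---|
| 3 / 1.5, 7.2 | −5.24 | −1.25 | −3.99 |
| 1.5 / 1, 4.8 | −1.62 | +0.29 | −1.91 |
| 3 / 1, 7.2 | −5.81 | +1.02 | −6.83 |
| 1 / 2, 4.8 | +0.62 | −2.47 | +3.09 |

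A separate simulation used a stronger contrast: log-odds slope 1.5 in the manual arm and 0.3 in the robot arm, 6 or 12 points per SD, 147 per arm and 2,000 runs per scenario. The spurious interaction averaged −4.5 to −9.8 points, with 11% to 39% rejection at a nominal 5%. Size and sign both depend on the assumptions.

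**The case against.** Several replies have force.

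- **The interaction test need not be biased.** A reader might infer that the interaction is wrong by up to 64% of the MCID (4.47 / 7). The working does not support that. The figure belongs to the arm contrast within a stratum under the most extreme equal-selection inputs, where the interaction is only −0.15. Interaction bias needs selection that differs by arm. The different targets make that plausible, but nothing in the protocol quantifies it.
- **The inputs are guesses.** The Introduction's 15% is the share of healthy knees with neutral HKA and joint line obliquity. It is not a restoration rate after manual TKA, so it cannot anchor the 15% used above, and milder rates shrink the bias.
- **The VELYS item carries its own restriction.** A reader might infer that an impossible interaction is definitely planned. The words limiting it to the raTKA group, the statement in the VELYS section that the data are for correlation with outcomes, and objective 2 all point to a within-arm association. This largely stands; what remains is that the sentence on interaction terms exempts nothing.
- **The primary analysis is a t-test** ("A Student's independent t-test will be used to compare mean scores between groups"), and one might infer that there is no model to extend. That fails: a two-sample t-test is a linear model with one binary covariate, and the Subgroup analyses section names a generalised linear model.
- **The analyses are labelled exploratory.** This lowers the stakes. It does not turn a post-randomisation split into a randomised comparison.

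None of these makes restoration a valid treatment-effect subgroup.

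**Conclusion.** The section is wrong as written on CPAK restoration and loosely worded on VELYS data. That restoration follows from allocation rests on the protocol's own timing and alignment targets, and that an allocation-by-VELYS term cannot be estimated rests on the data existing in one arm; neither depends on a simulation. The size of the restoration bias does depend on assumed inputs: about 0.4 to 4.5 FJS points within strata under equal selection, with an interaction close to zero, and a real interaction bias of either sign if selection differs by arm. Pre-operative CPAK group, in the same phrase, is a sound baseline factor. A reader should not infer that the primary result or the baseline subgroups are compromised; they are unaffected.

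**What to change.** In Subgroup analyses, state that allocation-by-subgroup interactions are limited to factors fixed before randomisation: age, sex, BMI, deprivation, primary compartment and pre-operative CPAK group. Fit them in the generalised linear model already named there. Remove CPAK restoration and VELYS data from that list and place them with the objective 2 analyses, as exploratory, non-randomised associations with outcome within each arm (robot arm only for VELYS data), with no allocation interaction. This costs protocol wording only: no new data, patients or assessments.

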### ***Sample size***

The sample size calculation is based on detecting a minimum clinically important difference (MCID) of 7 points in the FJS at six months post-operatively. This is informed by Alton et al (2025), and a standard deviation of 24 points, as reported in Clement et al., 2021. Using a one-sided alpha of 0.05 and a power of 80%, it was calculated that 147 participants per group would be required. To account for an anticipated 15% loss to follow-up, the final recruitment target is 173 participants per group, yielding a total study population of 346 participants.

Outcome data from the internal pilot (the first 100 study participants who have completed their 6-month follow-up) will be analysed. A blinded pooled estimate of the outcome variance will be computed and used in a pre-specified sample size re-estimation algorithm. The analysis team will remain blinded to treatment allocation; any sample size adjustments will be made according to the pre-specified rules to preserve type I error.

For the motion analysis sub-study, a sample size of 52 participants (26 in the raTKA and mTKA groups respectively) has been determined to provide sufficient power to detect expected differences in peak medial knee contact force compared with matched healthy controls.

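### BMI is specified in the exploratory subgroup model as a single cut at 35 kg/m², with no reason given and no continuous alternative

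*Protocol*

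**What the plan says.** All the relevant text is in the Subgroup analyses section of the protocol, which mentions BMI twice.

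- As a subgroup factor, with no cut and no functional form: "Predefined subgroup analyses will explore potential differences in outcomes according to: age; sex; BMI; socioeconomic deprivation level".
- As a model covariate: "A generalised linear model will be applied, incorporating allocation group, age, site, surgeon, gender, BMI". The bracket that follows immediately after these words sets the threshold at 35 kg/m² or more.

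Between the two stands the sentence on interactions: "These subgroup analyses will extend the primary models by including interaction terms and will be considered exploratory". Age is in the same covariate list without a threshold. The section promises sensitivity analyses on model assumptions and on fixed versus random effects, but does not mention the form of BMI.

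Two other places set the context. The eligibility criteria exclude BMI above 45 kg/m², so the group above the cut spans 35 to 45. The primary analysis, under Statistical analysis, has no covariates: "A Student's independent t-test will be used to compare mean scores between groups".

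**The concern.** BMI is measured as a continuous quantity. A single cut treats patients at 35 and 45 as identical, and patients at 34.9 and 35.1 as different. Where outcome or treatment benefit changes gradually with BMI, an indicator captures only part of that gradient. The covariate then adjusts less well, and a BMI-by-treatment interaction built on it is less precise than the collected data allow.

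The protocol names subgroup effectiveness as one of the NICE evidence domains the trial is meant to address, and BMI is a predefined subgroup factor. What is at stake is the precision of that exploratory analysis. The primary comparison and the sample size do not depend on it.

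This is more than detail left to a later analysis plan. The protocol states the threshold, and a consistent analysis plan would inherit it.

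**Working it through.** **1. The plan's own figure.** The Sample size section uses "detecting a minimum clinically important difference (MCID) of 7 points in the FJS at six months post-operatively" and "a standard deviation of 24 points", and reports: "Using a one-sided alpha of 0.05 and a power of 80%, it was calculated that 147 participants per group would be required".

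- Normal approximation: 2 × (24/7)² × (1.645 + 0.842)² = 145.4, so 146 per group.
- Exact t-test: 147 per group gives 80.2% power.
- Dropout: 147/0.85 = 172.9, so 173 per group, as stated.

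The stated numbers reproduce. The analysed total is 2 × 147 = 294. The protocol gives no figure for the BMI analysis itself.

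**2. Information kept by the cut.** For a linear effect, the share kept is the squared correlation between BMI and the indicator BMI ≥ 35. The protocol gives no BMI mean, SD or share above 35, so the distributions below are assumptions: normal, truncated to 17–45.

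| Assumed mean, SD | Share ≥ 35 | Information kept | Equivalent of 294 |
|---|---|---|---|
| 30, 5 | 16% | 0.445 | 131 |
| 31, 5.5 | 23% | 0.529 | 156 |
| 33, 6 | 36% | 0.616 | 181 |

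Over means 30–33 and SDs 5–6, about 45% to 62% is kept. With means 29–33, SDs 4.5–6, and a right-skewed (gamma) shape as well as the normal, the range is about 33% to 64%.

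Part of this loss comes with any cut. For an untruncated normal variable, even a split at the median loses about 36%.

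**3. What this means for the interaction.** Assume that the interaction uses the cut, that a share p of patients lies at or above 35, that allocation is 1:1, and that the residual SD is 24. The standard error of the difference in treatment effect between the two BMI groups is

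SE = 24 × √[4/(294p) + 4/(294(1−p))].

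- p = 0.15: SE = 7.84
- p = 0.20: SE = 7.00
- p = 0.25: SE = 6.46
- p = 0.30: SE = 6.11

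The interaction detectable with 80% power at two-sided 5% is 2.80 × SE, which is 22 points at p = 0.15 and 17 points at p = 0.30.

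Take a true difference of 7 points between the two BMI groups that arises from a linear gradient.

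- With the cut, power = Φ(7/SE − 1.96). This is Φ(0.893 − 1.96) = 14% at p = 0.15 and Φ(1.146 − 1.96) = 21% at p = 0.30.
- With continuous BMI, power = Φ(7/(SE√r) − 1.96), where r is the share of information kept for a normal variable with that p. At p = 0.15, r = 0.426 and power = Φ(1.367 − 1.96) = 28%. At p = 0.30, r = 0.576 and power = Φ(1.510 − 1.96) = 33%.

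**The case against.** **The cut is printed only for the covariate.** The subgroup list names BMI with no threshold, and no sentence says that the interaction uses 35 kg/m². A reader might infer that the protocol fixes BMI as binary throughout. That goes too far. The carry-over is the natural reading, because the interaction sentence and the model sentence are adjacent, but it remains an inference. This objection stands.

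**The size of the loss does not come from the protocol.** A reader might also conclude that most of the information, or a definite half of it, is lost. The documents support neither. The figure rests on an assumed BMI distribution and a linear effect. Over most of the narrower range above, slightly more than half is kept. If the effect really stepped at 35, the indicator would be the right form and nothing would be lost. This stands too, although the protocol gives no reason to expect such a step.

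**The consequence is small.** The analyses are labelled exploratory, the primary t-test does not use BMI, and the interaction is poorly powered in either form. A continuous term would not turn it into an informative test. This stands, and it limits the importance of the point.

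**The section leaves room for refinement.** It promises sensitivity analyses on model assumptions and allows further subgroup analyses to be pre-specified. Neither statement addresses how BMI is entered, so this softens the point without answering it.

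**Conclusion.** The point holds, as a minor one. The protocol specifies BMI in the exploratory model by a single threshold at 35 kg/m², gives no reason for it, and offers no continuous form. It probably applies the same threshold to the BMI-by-treatment interaction, but does not say so.

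The efficiency cost is conditional on a roughly linear effect and on the BMI distributions assumed above: about 45% to 62% of the information kept, or 33% to 64% on wider assumptions. The power comparison further assumes 15% to 30% of patients at or above 35, an SD of 24 and a two-sided 5% test. On those terms, continuous BMI raises power for a 7-point interaction from 14–21% to 28–33%. That is a real gain, but still well short of adequate. Nothing here bears on the primary estimate or the recruitment target.

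**What to change.** In the Subgroup analyses section of the protocol, state that BMI enters the model as a continuous term, linear or as a restricted cubic spline, both as a covariate and in the interaction with treatment. Keep the 35 kg/m² threshold only for displaying results by BMI group. A spline would also allow for a non-linear relation, at the price of a few degrees of freedom.

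The cost is one phrase in the model description. No new data are needed, and the primary analysis and sample size do not change.
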